Sample Size Calculation

The proposed sample size of 40 patients will be adequate to address the primary objective of evaluating the safety profile for Obizur. No formal sample size calculations were performed for the determination of the number of subjects for documentation, as this is primarily a descriptive study and is not designed to test a specific statistical hypothesis.

Planned Statistical Analysis

The analysis plan for reports will be fully described in a written and approved statistical analysis plan (SAP). Descriptive statistics will include specifically, but not exclusively, arithmetic mean, medians, standard deviations, minimum, maximum, proportions, frequency counts, 25th and 75th percentiles, and 95% confidence intervals of select point estimates. Figures will be prepared to illustrate data patterns over time where appropriate. Analyses will be performed using available data, though missing values are expected due to the non-interventional nature of the study. Full details on handling missing data, which are common in observational studies, will be described separately in the SAP.

SAEs will be described in listings and tables, and incidence rates will be calculated. Tables outlining the hemostatic effectiveness and immunogenicity of Obizur, frequency, total dose, and total number of infusions of Obizur required to control bleeding episodes will be developed. Tables displaying concomitant medications and patient comorbidities will also be developed. Time from symptoms to diagnosis to treatment will be reported.

Milestones:

The study will either end 4 years from the time the first patient is enrolled, or will be assessed at the point 40 patients have been enrolled in the prospective portion of the study, whichever is earlier.

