7. RATIONALE AND BACKGROUND

7.1 Medicinal Product Safety Profile

Acquired hemophilia A (AHA) is a rare autoimmune disorder in which non hemophilic persons develop auto-antibodies directed against circulating blood coagulation factor (F) VIII. These auto-antibodies are distinct from the alloantibodies that form in patients with congenital hemophilia A in response to factor replacement therapy. In approximately 50% of cases FVIII autoantibodies occur in patients with no concomitant disease, while the remaining cases may be associated with an underlying medical condition such as pregnancy, hematological or solid tumors, infections, use of medications, or autoimmune diseases such as systemic lupus erythematosus, rheumatoid arthritis, and thyroid disorders. The estimated incidence rate of AHA is approximately one case per million persons annually, though it is likely that this figure is underestimated in the elderly population. This presumption is underscored by evidence indicating that the incidence of AHA increases with age. The incidence rate in children under 16 years is estimated to be 0.045 per million persons annually, compared to an estimated rate of 14.7 per million persons annually in individuals over 85 years of age.

Patients with AHA often experience serious subcutaneous bleeding episodes in the muscles or soft tissues and mucous membrane. This varies from the clinical manifestations of patients with congenital hemophilia A in which bleeds into the joint spaces are common.^{4,5} Severe bleeds occur in up to 90% of patients with AHA and may result in an estimated mortality rate due to bleeding ranging from 3% to 22%.²

Treatment for AHA focuses on treating and preventing the occurrence of bleeding episodes and eradicating the autoantibodies. Treatment choice is dependent on the site and severity of the hemorrhage, patient characteristics, concomitant disorders, and inhibitor titer.³ On the whole, treatment modalities include normalization of factor deficiency via pFVIII, plasma, or recombinant FVIII, bypassing inhibitor activity with recombinant activated FVII (rFVIIa) or activated prothrombin complex concentrates (aPCCs), neutralization of the autoantibodies by high-dose immunoglobulin, and removal of the pathogenic autoantibodies by plasmapheresis or immunoadsorption.

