8.2 Primary Objective

The primary objective is to determine the incidence of therapy-related SAEs in patients with AHA who are prescribed and treated with Obizur in routine clinical practice.

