9.1.1 Primary Outcome

The primary outcome is patient safety in terms of AEs, their seriousness and severity. In particular, describing:

• Incidence of therapy-related SAEs and level of severity

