9.3.5 Safety (collect all SAEs; endpoint is therapy-related SAEs)

For the purpose of this study only serious adverse events (SAEs) will be collected. Reasons for collecting SAEs only include the following: Patients enrolled in this study are often elderly with a multitude of comorbidities and high medication intake. Additionally, they are seriously diseased receiving treatment in intensive care units. Thus, making qualified assessments of non-serious AEs with respect to isolated medicinal products is next to impossible given the multitude of treatments administered concomitantly.

- Key safety concerns:
 - > Inhibitor development against pFVIII (post baseline)
 - Date of inhibitor draw
 - > Hypersensitivity reactions including anaphylaxis
 - > Thrombogenicity
 - > Outcomes, including death (yes/no, date of death)

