9.7.3 Methods of Analysis

The analysis plan will be fully described in a written and approved SAP. Briefly, descriptive statistics will include specifically but not exclusively, arithmetic mean, medians, standard deviations, minimum, maximum, proportions, frequency counts, 25th and 75th percentiles, and 95% confidence intervals of select point estimates. Figures will be prepared to illustrate patterns of data over time where appropriate. Analyses will be performed using available data (missing values are expected due to the non-interventional nature of the study).

Therapy-related SAEs will be described in listings and tables and will presented by MedDRA system organ class (SOC) and preferred term (PT) and incidence rates will be calculated. Incidence will be interpreted as incidence proportion (number of patients with events/number of patients treated) and incidence rate (xx events per xx year of follow-up). Tables outlining the hemostatic effectiveness and immunogenicity of Obizur, frequency, total dose, total number of infusions of Obizur required to control bleeding episodes will be developed. Tables displaying concomitant medications and patient comorbidities will also be created. Time from symptoms to diagnosis to treatment will be reported. Where feasible, analyses may be performed within meaningful subgroups.

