9.7.3.1 Primary Outcome

The primary outcome (see Section 9.1.1) is patient safety in terms of AEs, their seriousness and severity. In particular, describing:

• Incidence of therapy-related SAEs and level of severity

These data will be described in tables and listings.

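### Section 9.7.3 plans SAE tables and incidence for therapy-related SAEs only, while the abstract plans them for SAEs without that limit; all-cause SAE incidence should stand beside the related figure

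*Protocol*

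**What the plan says.** The primary objective (Protocol section 8.2) is clear: "The primary objective is to determine the incidence of therapy-related SAEs in patients with AHA". The heading of section 9.3.5 separates what is collected from what is the endpoint: "Safety (collect all SAEs; endpoint is therapy-related SAEs". Under section 11.1.2 every SAE from Obizur treatment to study completion goes on the SAE form. Under section 11.1.2.2 the investigator places each one in one of four causality categories.

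On what will be analysed, two places differ:

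- Abstract, Planned Statistical Analysis: "SAEs will be described in listings and tables, and incidence rates will be calculated". There is no relatedness limit.
- Section 9.7.3: "Therapy-related SAEs will be described in listings and tables and will presented by MedDRA system organ class (SOC) and preferred term (PT"), followed by incidence as a proportion of treated patients and as a rate over follow-up time.

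Section 9.7.3.1 repeats the primary outcome of section 9.1.1. It opens broadly, "The primary outcome is patient safety in terms of AEs, their seriousness and severity", and then singles out one item: "Incidence of therapy-related SAEs and level of severity".

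The reason given in sections 9.3.5 and 11.1.2 for collecting only serious events is that the patients are often elderly, comorbid and in intensive care, so that "making qualified assessments of non-serious AEs with respect to isolated medicinal products is next to impossible given the multitude of treatments administered concomitantly".

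**The concern.** The abstract and the methods section cannot both define the main safety tables. If 9.7.3 governs, SAEs rated not related or unlikely related appear in no planned SAE table and in no incidence figure. With no control group, a related-only incidence can be read only through the attribution, and a reader could not see how many SAEs were set aside or how far the primary figure would move if some were judged differently.

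The protocol's own reason for omitting non-serious AEs sharpens this. Age, comorbidity, intensive care and many concurrent treatments are features of the patient, not of the seriousness of the event. The protocol does not explain why they would leave the attribution of SAEs unaffected, and section 9.9 names only recruitment as a limitation.

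**Working it through.** **Step 1. The texts side by side.**

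| Place | SAEs meant |
|---|---|
| Abstract, rationale | SAEs, no relatedness limit |
| Section 7.2, same sentence of the rationale | related SAEs |
| Abstract, planned analysis | SAEs, no relatedness limit |
| Section 9.7.3 | therapy-related SAEs |
| Sections 9.1.1 and 9.7.3.1 | AEs in general, with therapy-related SAEs singled out |
| Sections 9.3.5, 11.1.2 and 11.1.2.2 (collection) | all SAEs, each rated for causality |

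The split occurs twice, once in the rationale and once in the analysis, so it is not an isolated slip. The data needed for either version are collected.

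**Step 2. The protocol's planning figure (section 9.5).** Inputs: n = 40, assumed proportion 5%, so x = 0.05 × 40 = 2. The Clopper-Pearson limits are the 0.025 quantile of Beta(2, 39) and the 0.975 quantile of Beta(3, 38). Result: 0.61% to 16.92%, against 0.6% to 16.9% stated. The figure is reproduced. It measures sampling error only and contains nothing for error in attribution.

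**Step 3. One patient re-attributed.** 1/40 = 2.5%; 3/40 = 7.5%. A single changed judgement halves the primary proportion or raises it by half. Both values lie inside the interval of step 2.

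**Step 4. Background events in these patients.** Section 7.1 says that severe bleeds "may result in an estimated mortality rate due to bleeding ranging from 3% to 22"%. For 40 patients this is 0.03 × 40 = 1.2 to 0.22 × 40 = 8.8. The upper end exceeds the 2 patients in the planning numerator; the lower end does not. The range is background bleeding mortality in AHA, not an SAE rate under Obizur.

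**Step 5. Attribution error, by assumption.** The protocol gives no all-cause SAE proportion and no accuracy for the causality rating, so all inputs here are assumed. Let A be the proportion of patients with any SAE, T = 5% the proportion with a truly related SAE, se the chance that a related case is called related, and sp the chance that an unrelated case is called unrelated. The expected attributed proportion is T × se + (A − T) × (1 − sp).

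| A | se 0.9, sp 0.95 | se 0.7, sp 0.9 | se 0.5, sp 0.8 |
|---|---|---|---|
| 30% | 5.8% | 6.0% | 7.5% |
| 50% | 6.8% | 8.0% | 11.5% |
| 70% | 7.8% | 10.0% | 15.5% |

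For example, with A = 50% and the middle column: 0.05 × 0.7 + 0.45 × 0.1 = 0.035 + 0.045 = 8.0%. How far the primary figure is distorted depends on A, which a reader of related-only tables would not have.

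**Step 6. What an all-cause figure would look like.** With 40 patients, the exact 95% intervals are 16.6% to 46.5% for 12/40 (30%), 33.8% to 66.2% for 20/40 (50%) and 53.5% to 83.4% for 28/40 (70%). These proportions are also assumed. The figure would be imprecise but would not depend on the causality rating.

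**The case against.** The case for leaving the plan alone has real weight.

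- **A related-only endpoint is a deliberate choice.** It is stated consistently in sections 8.2 and 9.3.5. This stands, and nothing here asks for it to change.
- **A reader might infer that the protocol itself calls SAE attribution next to impossible.** It does not. The sentence is confined to non-serious AEs, and section 11.1.2.2 sets criteria for rating each SAE. Extending the limit to SAEs is an inference from the description of the patients.
- **A reader might infer that no all-cause information is planned anywhere.** That is too strong. The abstract plans incidence for SAEs without a limit, and 9.7.3.1 highlights therapy-related SAEs without excluding others.
- **A reader might infer that a drug effect on thrombosis or death would go unseen.** Sections 9.1.2 and 9.7.3.2 list any thrombogenic event, and the time until the bleed resolves, the patient dies or treatment is switched, with no causality filter. Section 9.3.5 also collects death and its date. Nor does the protocol say that thrombosis belongs to the natural course of AHA, so the point cannot rest on that.
- **Table content belongs to the SAP.** This is true of layout and row detail, and 9.7.3 calls itself brief. But 9.7.3 does not merely leave the matter open. It names a restricted set where the abstract names a wider one, and a SAP that followed 9.7.3 could omit all-cause SAEs and still conform to the protocol.
- **The shift from one patient lies well inside the planned interval.** This is correct. But that interval describes sampling error, and attribution error comes on top of it.

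**Conclusion.** The concern holds as an inconsistency with a consequence. Section 9.7.3 restricts the SAE listings, tables and incidence to therapy-related SAEs; the abstract does not. Under 9.7.3 the SAE incidence rests wholly on investigator attribution, and overall all-cause SAE incidence is not planned beside it.

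The size is moderate and only partly known. One judgement moves the planning proportion from 5% to 2.5% or 7.5%. Under the assumed error rates of step 5, a true 5% would be reported as anything from 5.8% to 15.5%. Background bleeding deaths may exceed the 2 planning cases, but need not.

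The conclusion assumes that the reasons given for non-serious AEs carry some force for SAEs in the same patients. The inconsistency between the two texts does not depend on that assumption. The sample size and the intervals in section 9.5 are unaffected.

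**What to change.** 1. In 9.7.3 and 9.7.3.1, align with the abstract: state that all SAEs regardless of causality are listed and tabulated by SOC and PT, with incidence proportion and incidence rate and with the causality category shown, beside the therapy-related SAEs. Say that therapy-related SAEs remain the primary endpoint.
2. Make the rationale in section 7.2 and in the abstract name the same set of SAEs.
3. In 9.9, add that attribution of SAEs to Obizur may be limited for the reasons already given for non-serious AEs.

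Cost: a few extra tables and some wording. Every SAE is already collected and rated, so sites have no added work. The downside is that a higher and less favourable all-cause figure will stand beside the primary one. In an uncontrolled study it will need a sentence saying that it includes events of the underlying disease and of other treatments.

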9.3.6 Bleed cessation assessment

- Overall effectiveness assessment for therapy response
 - > Bleeding stopped versus not stopped
 - Date bleeding stopped
 - ➤ If bleeding not stopped, note reason (e.g., death, new treatment)
- FVIII activity measurements throughout treatment
 - > Date assay performed
- Human and pFVIII antibody titers
 - ➤ Human and pFVIII antibody titers
 - Requirement to have a reference lab for anti-porcine FVIII antibody measurement (Central lab available if physician chooses to use it)

- Date and titer levels, starting at baseline through 180 days
- Concurrent bleeding episodes
 - Exacerbation of bleeding at an existing site
 - Date of exacerbation
 - Site of bleed
 - Appearance of bleeding at a new site
 - o Date
 - Site of bleed
- Treatment for bleeding episodes that occur greater than 72 hours after stopping cialuse treatment for the original bleed
 - ➤ Bleed start date
 - Bleed stop date
 - > Date of treatment
- Length of hospital stay per bleed (days)
 - ➤ Hospital admission/discharge dates
 - Location within hospital (ER, ICU, etc.)
 - Primary reason for hospitalization

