Bypassing agents such as rFVIIa and aPCCs are recommended as first-line treatment for acute bleeds due to demonstrated efficacy in the literature. ^{6,7,8} The choice of agent depends on several factors, including knowledge of the patient's previous response, convenience of dosing, use of plasma-derived products and cost. ⁹ Treatment with demopressin (DDVAP) may increase FVIII levels in some patients, though literature indicates that this treatment may be contraindicated in some patients due to

comorbidities. The international recommendations on the diagnosis and treatment of patients with AHA also recommend pFVIII as alternative therapy, however the drug was not available at the time of writing. Therefore, the authors indicated that the therapy may be added to an updated version of the guidelines after efficacy and safety had been established.

A recently developed highly purified antihemophilic recombinant porcine FVIII (rpFVIII) therapy (Obizur) was approved for the treatment of AHA. In AHA patients, Obizur temporarily replaces inhibited human FVIII with an rpFVIII based on the rationale that it is less susceptible to inactivation by circulating human FVIII antibodies. Twenty-nine adult subjects having autoimmune inhibitory antibodies to human FVIII and experiencing serious bleeding episodes that required hospitalization, were enrolled in a multi-center, prospective, open-label clinical trial that evaluated the safety and efficacy of Obizur. One of the subjects considered evaluable at study entry was later found to not have AHA, leaving 28 subjects evaluable for efficacy. Patients were treated with Obizur until resolution of bleeding or dosing was continued at the physician's discretion.

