9.1.2 Secondary Outcomes

Secondary outcomes will describe:

- Effectiveness assessment for resolution of bleeding, determined as either bleeding stopped or didn't stop
 - ➤ If bleeding did not stop, a reason should be provided (e.g., death)
- Time to bleeding resolution, death, or switch to another treatment.
- Number of Obizur units/kg required for control of bleeding (bleeding stopped)
- Number of Obizur infusions required for control of bleeding (bleeding stopped)
- Newly recognised anti-pFVIII inhibitors or increase in titer of anti-pFVIII
 inhibitors from pre-treatment level, impact on hemostatic efficacy and associated
 clinical manifestations if any, and evolution of titer over time
- Occurrence of hypersensitivity reactions
- Occurrence of any thrombogenic event

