9.3.4 Obizur Utilization

- Date and time of infusion
- Dose per infusion (U/kg)
- Total number of days of Obizur use

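### Bleed cessation is recorded by date only while infusions are timed, so infusions and dose given on the stop date cannot be placed before or after control

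*Protocol*

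**What the plan says.** - **Infusions.** Protocol section 9.3.4 lists "Date and time of infusion" together with the U/kg given at each infusion.
- **Cessation.** Section 9.3.6 lists stopped versus not stopped, "Date bleeding stopped", and "If bleeding not stopped, note reason (e.g., death, new treatment". The variable list in the Abstract (section 4) also gives cessation as a date.
- **Outcomes that need both records.** Section 9.1.2, repeated in 9.7.3.2, includes "Number of Obizur infusions required for control of bleeding (bleeding stopped" and the matching outcome in units/kg. They serve secondary objective 2 in section 8.3.
- **Time outcome.** The same sections list "Time to bleeding resolution, death, or switch to another treatment". Date of death is collected under section 9.3.5. No switch date is named as a variable; it would have to come from the medication records described in section 9.3.7.
- **Missing values.** Section 9.7.2 rules out imputation.

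**The concern.** To count what was required for control, each infusion must be ordered against the moment of control. The total given is not a safe substitute, because dosing may go on after bleeding has stopped. The protocol's account of the earlier Obizur trial says so: "Patients were treated with Obizur until resolution of bleeding or dosing was continued at the physician's discretion". In this study the treating physician sets the regimen (section 9.1), so the same can happen.

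With a stop date alone, the clock times of that day's infusions are of no use for the ordering. The problem is greatest for bleeds controlled quickly, where the stop date may hold most or all of the infusions. Time to resolution suffers too, since a calendar day is coarse for a bleed that stops within about a day. An analysis plan can choose a convention, but it cannot supply a time that was never recorded.

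**Working it through.** The protocol states no figure for infusions, dose or time to control, so there is none to reproduce. The confidence intervals in section 9.5 concern the safety proportion and play no part here.

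**Bounds for one episode.** Let *b* be the infusions before the stop date and *k* the infusions on it.

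- Lower bound on the count to control: max(1, *b*).
- Upper bound: *b* + *k*.
- Stop on the first treatment day (*b* = 0): the range is 1 to *k*, a gap of *k* − 1.
- Stop on a later day: from 0 to *k* of that day's infusions may precede control, a gap of *k*.

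The same bounds hold for U/kg, using the recorded dose of each infusion.

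**Illustration (assumed times).** Infusions at 10:00 and 18:00 on day 1 and at 02:00, 10:00 and 18:00 on day 2; stop date is day 2. Then *b* = 2 and *k* = 3, so the count lies between 2 and 2 + 3 = 5. Time from first infusion to cessation lies between 14 h (midnight at the start of day 2) and 14 + 24 = 38 h. The record cannot show whether bleeding stopped within 24 hours.

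**Average size.** This was simulated with 100,000 episodes per setting. Assumptions, none from the protocol: regular dosing every *h* hours continuing through the stop date, first infusion at a random clock time, and true stop time uniform over the first 1 or 7 days. The gap is the mean upper bound minus the mean lower bound. Percentages are the gap divided by the mean true count, from unrounded means.

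| Interval *h* | Largest gap | Stop within 1 day: true / lower / upper | Gap (%) | Stop within 7 days: true | Gap (%) |
|---|---|---|---|---|---|
| 4 h | 6 | 3.5 / 1.76 / 6.51 | 4.74 (136%) | 21.48 | 5.82 (27%) |
| 6 h | 4 | 2.5 / 1.44 / 4.49 | 3.05 (122%) | 14.51 | 3.87 (27%) |
| 8 h | 3 | 2.0 / 1.28 / 3.5 | 2.22 (111%) | 11.0 | 2.89 (26%) |
| 12 h | 2 | 1.5 / 1.12 / 2.5 | 1.38 (92%) | 7.5 | 1.91 (25%) |
| 24 h | 1 | 1.0 / 1.0 / 1.5 | 0.5 (50%) | 4.0 | 0.93 (23%) |

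For stop times spread over 2 days the gap is 50% to 82% of the true count, and over 4 days 35% to 45%.

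The bounds on a mean are the means of the individual bounds, so enrolling more patients does not narrow this gap. A known cessation time would close it.

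**The case against.** **The asymmetry suits a chart-based study.** Section 9.1 limits data to what already exists. An infusion is a discrete act with a time. Cessation is a judgement, and for the internal sites listed in section 9.3.2 the true moment may not be observable. A charted time may be only the time of the note. This stands in part: the field must be optional and its meaning stated. It does not justify leaving out a time that the chart does hold.

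**The outcomes may mean totals.** The closing parenthesis could define a subset, with total dose and infusions tabulated for episodes whose outcome was bleeding stopped. Objective 2 does speak of totals. That reading is possible and needs no clock time, but both the objective and the outcomes speak of what was required for control, and a total that includes later infusions does not measure that.

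**A reader might infer that the outcomes cannot be recovered at all.** The protocol does not support this. Every infusion on another date is classified exactly, the count and dose are bounded, and time to resolution is known in days. Likewise, a six-fold range (1 to 6) needs both an assumed six infusions on the first treatment day and cessation on that day.

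**A reader might also infer that resolution, death and switch are pooled into one uninterpretable time.** The bullet names three endpoints and does not say they will be pooled. Status, reason if not stopped, stop date and date of death are collected separately, so the endpoints can be told apart. How competing events are handled belongs to the SAP, which is not shown. What remains is that no switch date is named.

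**Conclusion.** The mismatch is real and lies in data collection. For the two outcomes on what was required for control, the ambiguity is at most the infusions, and their U/kg, given on the stop date. Under assumed 24- to 4-hourly dosing its average is about 50% to 136% of the mean true count for bleeds controlled within a day, and 23% to 27% if stop times spread over seven days. These sizes rest on regular dosing that continues through the stop date and on uniform stop times; the protocol gives neither a dosing interval nor a distribution of stop times. Time to resolution is known only to a window of up to 24 hours.

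Severity is minor. The outcomes are secondary and descriptive, effectiveness is to be described only where data are available (section 9.1), and the primary safety outcome is untouched.

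**What to change.** In section 9.3.6, and in the matching variable list of the Abstract:

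1. Replace the stop-date item with: date and, if documented, time at which bleeding was first recorded as stopped, or the last infusion before that record.
2. Add the date, and time if documented, of any switch to another treatment.
3. Count infusions and U/kg for infusions started up to the recorded point. Where no time is charted, use the date, flag the episode, and report lower and upper bounds. This needs no imputation and so agrees with section 9.7.2.

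The cost is a time field and a switch date on the case report form, with no added visit or test. The drawback is that some charts will lack a time or give only the time of the note, so the precision gained will vary between patients.
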